### 10.5.3. Efficacy

#### 10.5.3.1. ELLIPTA Device Sensor Assessments

Percentage of ELLIPTA doses taken (daily adherence) Endpoint
Overview of Calculation

 
1. Create a dataset (Observed Data A) to calculate the monthly observed percentage of ELLIPTA adherence values (from month 1 to month 6) accounting for the following, 
 
a. number of days adherent to ELLIPTA (as prescribed)
 
b. number of days post ELLIPTA maintenance sensor permanent discontinuation
 
c. the intermittent missing daily adherence data due to device incident.
 
d. Non-adherent days (i.e. none of the above and those days with more than one dose in 24-hour period).
 
 
 

Percentage of ELLIPTA doses taken (daily adherence) Endpoint

2. Duplicate the observed monthly adherence values dataset (Observed Dataset A). Using the values in the duplicate dataset (Dataset B), impute the month where the sensor was permanently discontinued before the end of that month (and therefore presents a monthly adherence rate based on partly observed sensor data for that month) as missing unless the participant is a study completer.
 
3. Using each of the two observed datasets (Observed Dataset A and Observed Dataset B), create four separate imputed datasets (J2R-Dataset A, J2R-Dataset B, MAR-Dataset A, MAR-Dataset B) that account for the two imputation methods (J2R or MAR) that may be applied to participants' data after discontinuation of the maintenance sensor, ELLIPTA or withdrawal from study. Imputation will be carried out using observed monthly adherence rates for months 1 to 6. 1000 draws will be used. Completely missing intermediate monthly values will be assumed MAR. The multiple imputation will be implemented using the methods described in Carpenter, 2013, using the macros (Part1A, Part1B, Part2A and Part2B) available from https://missingdata.lshtm.ac.uk/2017/04/06/gsk-five-macros/ using seeds documented in the RAP for the respective endpoint.
 
4. The Observed Datasets (A and B), imputed datasets (J2R-Dataset A, J2R-Dataset B, MAR-Dataset A, MAR-Dataset B) and the timing of the intercurrent events; permanent discontinuation of the ELLIPTA maintenance sensor; permanent discontinuation of ELLIPTA treatment and withdrawal from study; will be used to create an analysis dataset (Dataset C) that identifies the proportion of each month to be assigned as observed data, J2R imputed data, MAR imputed data, or no data. The strategy for handling intercurrent events is described in Section 7.1.4 Strategy for Intercurrent (Post-Randomisation) Events.
 
Within each imputation draw, for each missing month, the observed and any imputed data will be combined to provide a percentage adherence value. The values for months 4 to 6, months 1-3 and months 1-6, will be combined to create the value for the respective primary and secondary endpoint analyses and the weight to be assigned to each participant.
 
5. Analyse using Multiple Imputation macro Part3
 

Perform ANCOVA on the endpoint for each imputed dataset to obtain treatment effect estimate and standard error

Combine estimates across imputations using Rubin's rules


### Percentage of ELLIPTA doses taken (daily adherence) Endpoint

The intercurrent events identified as part of the primary endpoint estimand and derivation are detailed in full in Section 7.2.1.3 Strategy for Intercurrent (Post-Randomisation) Events. Below are two schematics of the intercurrent event patterns and their estimation rules.

#### Intercurrent Event Patterns

		6 months	
A. Completer			e E S
B. Discontinuation of sensor only		e	E S
C. Discontinuation of sensor prior to ELLIPTA discontinuation		e	E S
D. Concurrent discontinuation of sensor and ELLIPTA without concurrent withdrawal from the study		e E	S
E. Concurrent discontinuation of sensor and ELLIPTA and withdrawal from study		e E S	
		e Discontinuation of ELLIPTA maintenance sensor	
		E Discontinuation of ELLIPTA	
		S Withdrawal from study	

#### Intercurrent Event 'Estimation Rules' 1-4

		6 months	
A. Completer		Observed from ELLIPTA maintenance sensor	e E S
B. Discontinuation of sensor only		Observed from ELLIPTA maintenance sensor	e J2R imputation E S
C. Discontinuation of sensor prior to ELLIPTA discontinuation		Observed from ELLIPTA maintenance sensor	e J2R imputation E S No data / J2R a
		Observed from ELLIPTA maintenance sensor	e J2R imputation E No S data
		Observed from ELLIPTA maintenance sensor	e J2R imputation E No data S
D. Concurrent discontinuation of sensor and ELLIPTA without concurrent withdrawal from the study		Observed from ELLIPTA maintenance sensor	e No data S
		Observed from ELLIPTA maintenance sensor	e No data S
E. Concurrent discontinuation of sensor and ELLIPTA and withdrawal from study		Observed from ELLIPTA maintenance sensor	e No data / J2R / MAR b S
		e Discontinuation of ELLIPTA maintenance sensor	
		E Discontinuation of ELLIPTA	
		S Withdrawal from study	

a. No data if withdrawal related to ELLIPTA; J2R imputation if withdrawal not related to ELLIPTA

b. No data if withdrawal related to ELLIPTA; J2R imputation if withdrawal related to CIS; MAR imputation if withdrawal not related to ELLIPTA or CIS

Percentage of ELLIPTA doses taken (daily adherence) Endpoint
Intercurrent Events related to Relvar/Breo or CIS
In order to implement the intercurrent event strategy detailed in Section 7.1.4 Strategy for Intercurrent (Post-Randomisation) Events, it is necessary to determine if and when the reasons for permanent discontinuations related to CIS or ELLIPTA Relvar/Breo treatment occur.
The date and reason for permanently withdrawing from ELLIPTA treatment will be determined from the study treatment (Relvar/Breo ELLIPTA) discontinuation page of the eCRF.
ELLIPTA discontinuation reasons classified as not related to ELLIPTA are as follows:

• AE - not treatment related (determine from the AE that lead to withdrawal to treatment if study treatment related, on the AE eCRF page)

• Protocol deviation - not related to study treatment

• Participant reached protocol defined stopping criteria - not related to study treatment

• Study closed/terminated

• Lost to follow-up

• Investigator discretion - not related to study treatment

• Decision by participant or proxy - not related to study treatment

ELLIPTA discontinuation reasons classified as related to ELLIPTA are as follows:

• AE - treatment related (determine from the AE that lead to withdrawal to treatment if study treatment related, on the AE eCRF page)

• Lack of efficacy

• Protocol deviation - related to study treatment

• Participant reached protocol defined stopping criteria (except pregnancy) - related to study treatment

• Investigator discretion - related to study treatment

• Decision by participant or proxy - related to study treatment

The date and reason for withdrawing from the study will be determined from the study conclusion page of the eCRF.
Study discontinuation reasons classified as related to CIS are as follows:

• Withdrew consent – dissatisfaction with the connected inhaler system (CIS)

Percentage of ELLIPTA doses taken (daily adherence) Endpoint
Monthly Percentage of ELLIPTA doses taken (daily adherence) - Calculation

STEP 1: Creating the observed adherence dataset (Observed Dataset A)
 
To determine the monthly observed percentage of ELLIPTA adherence values (Observed Dataset A) the following should be applied for each month:
 
For Baseline Analysis Month, for each participant create a count of each of the following types of Days
 
D1 = Adherence recorded  D2 = Device incident  D3 = Post discontinuation of maintenance Sensor  D4 = Non-adherent (including those imputed as non-adherent)
 
 
• D5=D1 + D2 + D3 + D4, i.e. The total number of days within the Baseline Analysis Month; the total number of days between Beginning Timepoint and Ending Timepoint as defined in Table 5 in Section 10.2 Appendix 2: Assessment Windows.
 
 
For Analysis Month 1, 2, 3, 4 and 5, for each participant create a count of each of the following types of days:
 
D1 = Adherence recorded  D2 = Device incident  D3 = Post discontinuation of maintenance Sensor  D4 = Non-adherent (including those imputed as non-adherent)
 
D5 = D1 + D2 + D3 + D4, i.e. The total number of days within the Analysis Month; the total number of days between Beginning Timepoint and Ending Timepoint as defined in Table 5 in Section 10.2 Appendix 2: Assessment Windows.
 
For Analysis Month 6, for each participant create a count of each of the following types of days:
 
D1 = Adherence recorded  D2 = Device incident  D3 = Post discontinuation of maintenance sensor  D4 = Non-adherent (including those imputed as non-adherent)
 
D5 = D1 + D2 + D3 + D4, i.e. the total number of days within Analysis Month 6; the total number of days between Beginning Timepoint and Ending Timepoint as defined in Table 5 in Section 10.2 Appendix 2: Assessment Windows.
 
The following observations from the sensor and eCRF will be required to determine the above Days and the differences between missing at random due to device/sensor incident and non-adherent days.
 
 
• Device malfunction date
 
• Sensor malfunction date
 
• Permanent discontinuation of maintenance sensor
 
• First and last individual sensor synchronisation dates
 
 
The first and last individual sensor synchronisation dates will be provided in the sensor dataset. These dates will be used to assess whether missing observations are due to non-adherent days or data being missing at random due to device/sensor malfunction.
 
For each Analysis Month, the Observed adherence for that month will be calculated as follows:


Percentage of ELLIPTA doses taken (daily adherence) Endpoint
$\text{Monthly observed maintenance adherence (\%)} = \left( \frac{D1}{D5 - D2 - D3} \right) \times 100$

STEP 2: Creating the modified observed adherence dataset (Observed Dataset B)
 
The Observed Dataset A will be duplicated. Using the values in the duplicate dataset (Observed Dataset B) the Analysis Month where the maintenance sensor was permanently discontinued before the end of that month (and therefore presents a monthly adherence rate based on partly observed sensor data for that month) will be imputed as missing; i.e. in Dataset B, if within an Analysis Month (<math>D3 > 0</math> and <math>D3 < D5</math>) then set monthly value for that Analysis Month to missing. (Note: unless the participant is a completer in which case do not set the value to missing for that Analysis Month)

STEP 3: Creating the reference imputed datasets under MAR and J2R method
 
Using each of the two observed datasets (Observed Dataset A and Observed Dataset B) monthly values, create four separate reference imputed datasets (J2R-Dataset A, J2R-Dataset B, MAR-Dataset A, MAR-Dataset B) that account for the two imputation methods (J2R or MAR). Completely missing intermediate monthly values will be assumed MAR.
 
The multiple imputation will be implemented using the methods described in Carpenter, 2013 using macros, Part1A, Part1B, Part2A and Part2B (available from https://missingdata.lshtm.ac.uk/2017/04/06/gsk-five-macros/). The seeds are documented at the end of Section 10.5.3.1. and 1000 draws will be used in the relevant macros parameters.
 
Due to the range of the monthly adherence percentages being limited between 0 and 100, the multiple imputation process can generate percentages outside the possible range of values (< 0% or > 100%). A cap will be put in place where values imputed < 0 will be set as 0 and values imputed as > 100 set as 100.


STEP 4: Creating the Monthly Analysis values dataset
 
For each month within each participant create a count of each of the following durations based on intercurrent events: Let,
 
<math>m1</math> = maintenance sensor still in use
 
<math>m2</math> = maintenance sensor discontinued, but ELLIPTA Relvar/Breo not discontinued
 
<math>m3</math> = ELLIPTA Relvar/Breo discontinued (includes days post withdrawal from the study). Note, if participant is a completer then for Analysis Month 6, <math>m3=0</math>.
 
<math>m4 = m1 + m2 + m3</math>
 
Calculate the proportion of days the sensor was still in use from the total number of days ELLIPTA was in use within a month, <math>m1/(m1+m2)</math>
 
Calculate the proportion of days the sensor was discontinued from the total number of days ELLIPTA was in use within a month, <math>m2/(m1+m2)</math>
 
Set participants monthly values to observed, MARA, MARB, J2RA, J2RB imputation, no data each with an <math>m1</math>, <math>m2</math>, <math>m3</math> and <math>m4</math> duration.

Percentage of ELLIPTA doses taken (daily adherence) Endpoint												
--	--	--	--	--	--	--	--	--	--	--	--	--

Examples include to following:

- A participant who prematurely discontinues sensor after 15 days of Analysis Month 5 and concurrently discontinues ELLIPTA maintenance therapy and study withdrawal after 10 days of Analysis Month 6

Subject Id	Draw	Month	A	B	J2RA	J2RB	MARA	MARB	m1	m2	m3	m4
X	1	1	77	77	77	77	77	77	28	0	0	28
X	1	2	82	82	82	82	82	82	28	0	0	28
X	1	3	87	87	87	87	87	87	28	0	0	28
X	1	4	77	77	77	77	77	77	28	0	0	28
X	1	5	71	.	71	77	71	78	15	13	0	28
X	1	6	.	.	80	79	77	76	0	10	18	28

- A participant who concurrently prematurely discontinues sensor, ELLIPTA maintenance therapy and study withdrawal after 15 days of Analysis Month 5

Subject Id	Draw	Month	A	B	J2RA	J2RB	MARA	MARB	m1	m2	m3	m4
X	1	1	77	77	77	77	77	77	28	0	0	28
X	1	2	80	80	80	80	80	80	28	0	0	28
X	1	3	79	79	79	79	79	79	28	0	0	28
X	1	4	75	75	75	75	75	75	28	0	0	28
X	1	5	83	.	83	77	83	79	15	0	13	28
X	1	6	.	.	77	77	75	80	0	0	28	28

- A participant who completes the study after 26 days in Analysis Month 6

Subject Id	Draw	Month	A	B	J2RA	J2RB	MARA	MARB	m1	m2	m3	m4
X	1	1	77	77	77	77	77	77	28	0	0	28
X	1	2	82	82	82	82	82	82	28	0	0	28
X	1	3	87	87	87	87	87	87	28	0	0	28
X	1	4	77	77	77	77	77	77	28	0	0	28
X	1	5	80	80	80	80	80	80	28	0	0	28
X	1	6	82	82	82	82	82	82	15	11	0	26

- If the sensor is in use for at least a day within a month, m1>0 then let the analysis value be a combined value (weighted average) of the J2RA observed and J2RB imputed values, by taking a proportion of each value based on the proportion of days sensor was still in use and discontinued whilst on ELLIPTA respectively;

Analysis value =  $m1/m1+m2 \times (\text{value from J2RA}) + m2/m1+m2 \times (\text{value from J2RB})$

Note the weight is,  $m1 + m2$

- Else if the sensor was not used in the month, m1=0 then let the analysis value be the imputed value,

Analysis value = value from J2RA dataset (which is the imputed value)

Implement special cases of J2R post-discontinuation of ELLIPTA by identifying participants where ELLIPTA is prematurely discontinued and the participant concurrently withdraws from the study, and ELLIPTA discontinuation reason is not related to ELLIPTA:

Percentage of ELLIPTA doses taken (daily adherence) Endpoint

 
If the sensor is in use for at least a day within a month, <math>m1>0</math> then let the analysis value be a combined value (weighted average) of the J2RA observed and J2RB imputed values, by taking a proportion of each value based on the proportion of days the sensor is in use and not in use in that month  <math display="block">\text{Analysis value} = m1/m4 \times (\text{value from J2RA}) + (m2+m3)/m4 \times (\text{value from J2RB})</math> Note the weight is, <math>m4</math>
 
Else if the sensor was not used in the month, <math>m1=0</math> then let the analysis value be the imputed value,  <math display="block">\text{Analysis value} = \text{value from J2RA dataset (which is the imputed value)}</math>
 
 
Implement special case of MAR post-discontinuation of ELLIPTA by identify participants where ELLIPTA is prematurely discontinued and the participant concurrently discontinues the maintenance eSensor and concurrently withdraws from the study, and ELLIPTA discontinuation reason is not related to ELLIPTA and study withdrawal is not related to CIS.
 
Where ELLIPTA has not been discontinued after the sensor but on the same day, <math>m2=0</math>.
 
 
If the sensor is in use for at least a day within a month, <math>m1>0</math> then let the analysis value be a combined value (weighted average) of the J2RA observed and MARB imputed values, by taking a proportion of each value based on the proportion of days the ELLIPTA was in use and not in use in that month  <math display="block">\text{Analysis Value} = m1/m4 \times (\text{value from J2RA}) + m3/m4 \times (\text{value from MARB})</math>
 
Else  <math display="block">\text{Analysis Value} = m1/m4 \times (\text{value from J2RA}) + m3/m4 \times (\text{value from MARA})</math>
 
 
Note the weights are <math>m4</math>


STEP 5: Primary and Secondary Percentage of ELLIPTA doses taken Endpoints calculation
 
The calculations presented in the previous steps support the final derivation of the following primary and secondary endpoints, the percentage of ELLIPTA doses taken between
 
 
the beginning of Month 4 and the end of Month 6
 
the beginning of Month 1 and the end of Month 6
 
the beginning of Month 1 and the end of Month 3
 
 
For participants who complete the study treatment (i.e. no premature discontinuation of ELLIPTA Relvar/Breo) during the endpoint period of interest:
 
Analysis Endpoint is the average of monthly Analysis Values over the number of months in the endpoint period of interest, i.e.
 
 
Month 4 to Month 6
 
Month 1 to Month 6
 
Month 1 to Month 3
 
 
For participants who prematurely discontinue ELLIPTA during the endpoint period of interest for reasons related to ELLIPTA, then the weight is the total duration on ELLIPTA within the endpoint period of interest and applied to each analysis month based on the duration within that month. This weight should be applied to each monthly Analysis value within the period of interest and results summed together to produce the final endpoint/response variable for modelling within macro Part 3.

Percentage of ELLIPTA doses taken (daily adherence) Endpoint
---

Note the weight is, total duration of ELLIPTA use within the period of interest . The proportion of weight to apply per monthly Analysis value is  $m1+m2/\text{total duration of ELLIPTA use within the period of interest}$

For participants who prematurely discontinue ELLIPTA during the endpoint period of interest for reasons not related to ELLIPTA or CIS, or just related to CIS, the MAR or J2R imputation assumes participants would have continued taking ELLIPTA until the end of the period of interest. The weight is the total duration within the endpoint period of interest. This weight will be applied to each monthly Analysis value within the period of interest and results summed together to produce the final endpoint/response variable for modelling within macro Part 3.

Note the weight is, total expected ELLIPTA duration within the period of interest. The proportion of weight to apply per monthly Analysis value is  $m1+m2+m3/\text{Total expected ELLIPTA duration within the period of interest}$ .

Percentage of ELLIPTA doses taken (daily adherence) – Sensitivity Analysis
---

Sensitivity analyses will be performed estimating the treatment effect by utilizing a generalized linear model (GLM) and not running the multiple imputation process. The model will follow a binomial distribution with the logit link function.

The sensitivity analyses will be performed for the following primary and secondary endpoints relating to the percentage of ELLIPTA doses taken between

- the beginning of Month 4 and the end of Month 6
- the beginning of Month 1 and the end of Month 6
- the beginning of Month 1 and the end of Month 3

Model assumptions will be checked by using standardised residual plots. Missing data will be assumed to be MAR.

The weighting strategy is to be applied as detailed above.

Percentage of ELLIPTA doses taken (daily adherence) Endpoint
---

Seeds for Multiple Imputations Macros
--

Seeds for all planned MI analyses were determined in advance using the following SAS code and documented within this RAP prior to unblinding:

```
data temp;
do i = 1 to 6;
  number=round(10000*ranuni(0),1);
  output;
end;
run;
proc print;
run;
```

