#### **7.1.4.2. Events following premature discontinuation of the ELLIPTA maintenance sensor**

It is assumed that participants would continue to take ELLIPTA as they would have without the CIS intervention (J2R imputation) following discontinuation of the ELLIPTA maintenance sensor.

It is assumed that ELLIPTA treatment is no longer appropriate if the participant discontinues ELLIPTA but remains in the study or withdraws for a reason related to ELLIPTA. The ELLIPTA adherence endpoint is no longer considered relevant and subsequent follow-up is excluded from the analysis, with participants weighted in the analysis by the proportion of months 4 to 6 for which data is included.

It is assumed that participants would continue to take ELLIPTA as they would have with their allocated CIS intervention (MAR imputation) following concurrent discontinuation of the ELLIPTA maintenance sensor and withdrawal unrelated to ELLIPTA or CIS.

See Section 10.5.3.1 ELLIPTA Device Sensor Assessments for further derivation details.

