**Table 5 Sensor Data Assessment Windows**

Sensor Data Assessment Windows		
Analysis Month	Analysis Period	
	Beginning Timepoint	Ending Timepoint
Baseline	Latest of either Day -28 or day after Visit 1 (minimum of 14 days must be present to create a baseline)	Day -1 (Day prior to randomisation)
1	Day 1 (Day of randomisation)	Day 28 or discontinuation from adherence/rescue assessment if within month 1
2	Day 29	Day 56 or discontinuation from adherence/rescue assessment if within month 2
3	Day 57	Day 84 or discontinuation from adherence/rescue assessment if within month 3
4	Day 85	Day 112 or discontinuation from adherence/rescue assessment if within month 4
5	Day 113	Day 140 or discontinuation from adherence/rescue assessment if within month 5
6	Day 141	Earliest of either day of visit 10, Day 168 or discontinuation from adherence/rescue assessment if within month 6 if participant is a completer  OTHERWISE  Day 168 or discontinuation from adherence/rescue assessment if within month 6
Note: 'Discontinuation from adherence/rescue assessment' occurs at the earliest of premature discontinuation from use of the ELLIPTA /MDI sensor, premature discontinuation of ELLIPTA (for adherence measures), or premature withdrawal from the study.		

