## 10.6. Appendix 6: Reporting Standards for Missing Data

### 10.6.1. Premature Withdrawals

Element	Reporting Detail
General	
 
Participant study completion (as specified in the protocol) is defined as completing all visits of the study including the follow-up phone contact.
 
Withdrawn participants will not be replaced in the study.
 
All available data from participants who are withdrawn from the study will be included in listings and where possible any available data from withdrawn participants will be included in summaries or analyses, unless otherwise specified.
 

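### SAP 10.5.3.1: participants who stop only the ELLIPTA sensor and complete the study keep their own adherence, not a jump-to-reference value, for the rest of the stopping month; Table 5 also disables the Step 2 trigger

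*SAP*

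**What the plan says.** **The estimand.** SAP Table 3, rule 2, assigns J2R to participants who stop the ELLIPTA maintenance sensor only. Section 7.1.4.2 repeats this. In the 10.5.3.1 schematic, pattern B (sensor stopped early, ELLIPTA and study continuing to 6 months) shows J2R for all time after the sensor stops. SAP Table 1 explains that the J2R trigger was moved from study withdrawal to sensor discontinuation because the sensor can be stopped without leaving the study.

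**The derivation.** Step 2 copies Observed Dataset A to Dataset B. If the sensor stopped part-way through a month (D3>0 and D3<D5), the program is to "then set monthly value for that Analysis Month to missing", "unless the participant is a completer in which case do not set the value to missing for that Analysis Month". The overview at the start of 10.5.3.1 gives the same exemption: the stopping month is imputed "as missing unless the participant is a study completer". Section 10.6.1 says study completion "is defined as completing all visits of the study including the follow-up phone contact"; it does not mention sensor use.

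Step 4 then forms the monthly value as m1/(m1+m2) × J2RA + m2/(m1+m2) × J2RB, where m1 is days on the sensor and m2 is days off the sensor but still on ELLIPTA.

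**The day counts.** Step 1 defines D5 as D1+D2+D3+D4 and also as "the total number of days between Beginning Timepoint and Ending Timepoint as defined in" Table 5. Table 5 ends Month 4, for example, at "Day 112 or discontinuation from adherence/rescue assessment if within month 4", and its note counts sensor discontinuation as such a discontinuation.

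**The concern.** There are two defects in the primary-endpoint derivation.

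1. Everyone who stops only the sensor and attends all remaining visits is a study completer under 10.6.1. Step 2 exempts exactly these people. Their stopping month stays non-missing in Dataset B, so the imputation has nothing to fill and J2RB equals the observed value. The off-sensor days then carry the participant's own adherence, where rule 2 calls for a control-arm value.

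2. If a month ends on the day the sensor stops, D5 contains no post-discontinuation days. D3 is then 0, and D3>0 and D3<D5 cannot be true for anyone, completer or not.

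Two programmers, one following the text and one the worked examples, could produce different primary analysis datasets.

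**Working it through.** **Inputs from the SAP (Step 4 worked examples)**
- Example 1, a non-completer, Month 5: A = 71, B missing, J2RA = 71, J2RB = 77, m1 = 15, m2 = 13.
- Example 3, titled "A participant who completes the study after 26 days in Analysis Month 6", Month 6: A = B = J2RA = J2RB = 82, m1 = 15, m2 = 11. Months 4 and 5 are 77 and 80.

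**Reproducing the SAP's figures**
- Example 3 as written: 15/26 × 82 + 11/26 × 82 = 82.0. The Months 4-6 mean is (77 + 80 + 82)/3 = 79.7. The 11 off-sensor days contribute the participant's own 82.
- Example 1: 15/28 × 71 + 13/28 × 77 = 73.8. Here B was set to missing, and the J2R value does enter.

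**Example 3 with rule 2 applied.** The SAP gives no J2R draw for this participant, so one must be assumed. Take 66, the control-group mean of the earlier adherence study cited in protocol 11.2.2:
- Month 6: 15/26 × 82 + 11/26 × 66 = 75.2.
- Months 4-6 mean: (77 + 80 + 75.2)/3 = 77.4, which is 2.3 points below 79.7.
- For assumed J2R values from 60 to 79, the mean runs from 76.6 to 79.2, or 3.1 to 0.4 points lower.

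**Which days are affected.** Only the stopping month is. In later months m1 = 0, and Step 4 uses the J2RA value, which is imputed. A stop in Months 1-3 therefore leaves the primary endpoint untouched by the exemption, although it affects the Month 1-3 and Month 1-6 endpoints. A stop in Months 4-6 affects at most 27 of 84 days, and 14 on average if the stop day is uniform within the month.

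**Arm-level size.** Shift = share stopping in Months 4-6 × affected days/84 × gap. Shares and gap are assumptions; the 15-point gap borrows the design difference.

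| Share of Arm 1 | Days | Gap | Shift (points) |
|---|---|---|---|
| 5% | 14 | 15 | 0.05 × 14/84 × 15 = 0.125 |
| 10% | 14 | 15 | 0.10 × 14/84 × 15 = 0.25 |
| 2% | 14 | 15 | 0.05 |
| 10% | 27 | 15 | 0.48 |

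If 5% or 10% is instead the share stopping at any time, uniformly over six months, the 14-day figures halve to about 0.06 and 0.13. For scale, the planned standard error of the difference is 28 × √(2/76) = 4.5 points.

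**The Table 5 conflict.** Read literally, example 1's Month 5 would end on day 15, giving D3 = 0, B = 71 and a monthly value of 71.0. The example instead shows B missing, a month length (m4) of 28 and, by Step 4, 73.8. Example 2 likewise has B missing with m4 = 28.

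**The case against.** The strongest reply is that completer in Step 2 may mean pattern A of the schematic, where sensor, ELLIPTA and study all end together at 6 months. Pattern B would then not be exempt and rule 2 would apply in full. The Step 4 note setting m3 = 0 for completers is limited to Month 6, which suggests an end-of-study purpose. Example 3 may also be a slip: its title does not mention stopping the sensor, and the rescue completer example in 10.5.3.2 also has 15 sensor days although the other rescue examples use 20.

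This is plausible as intent, but it is not what the text says. The overview says study completer, 10.6.1 defines completion by visits, the Step 2 exemption has no month limit, and the only completer example has 11 off-sensor days. Under the pattern A reading the exemption would also have no function, because Table 5 already ends a completer's Month 6 at Visit 10 if that comes before Day 168.

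On Table 5, the intent is visible: D5 includes D3 by formula, examples 1 and 2 use full months, and the adherence listing shell counts post-discontinuation days. The observed monthly percentage, D1/(D5−D2−D3), is the same either way. That stands; the passages still contradict each other on the Step 2 trigger.

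A reader might infer that the primary derivation fails to implement rule 2 altogether, or that it is biased in one direction towards CIS. The documents support neither. Whole months after the stop do receive J2R. Direction depends on whether the stopper's own adherence lies above the J2R value: people who abandon the sensor may adhere poorly, and the SAP's illustrative rows go both ways (71 against 77 in example 1, 83 against 77 in example 2).

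**Conclusion.** Both inconsistencies are real and should be corrected, but their effect is small. As written, Step 2 gives sensor-only stoppers who complete the study their own adherence for the rest of the stopping month, against rule 2, 7.1.4.2 and pattern B. Table 5 and the definition of D5 separately make the Step 2 trigger unreachable, against examples 1 and 2.

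On the primary difference the exemption is worth about 0.13 to 0.25 point under the central assumptions, roughly 3% to 6% of one planned standard error. The documents give neither the share of sensor-only stoppers nor the gap. The expected direction favours the CIS arms if on-CIS adherence exceeds the control-based value. In Arm 5, J2R draws on the same arm, so little changes there. This would rarely alter a conclusion, and the planned sample size is unaffected.

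**What to change.** - **Step 2 and the overview in 10.5.3.1:** delete the completer exemption. Alternatively, restrict it explicitly to pattern A participants whose sensor use ends at Visit 10 or study end. Deletion is cleaner, because a Month 6 that ends at Visit 10 leaves those participants no post-stop days to exempt.
- **Table 5 and Step 1:** for D5, let every month run to its last study day (Month 6: the earlier of Visit 10 and Day 168 for completers). Use the discontinuation date only to start counting D3.
- **Third worked example:** if the 11 off-sensor days are kept, show B as missing and J2RB as an imputed value. If an ordinary completer was meant, set m1 = 26 and m2 = 0.
- **SAP 10.5.3.2 (rescue-free days):** make the same changes to the overview, Step 2 and the completer example, which has r1 = 15, r2 = 12 and B = 82.

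The cost is SAP wording plus one condition and one date rule in the derivation programs, with no new data. It should be settled before unblinding.
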